### 6.2.3 During visit interventions

Providers will receive clinical decision support within relevant patients' charts that highlight the patient's under-treated blood pressure and its consequences and potential impacts of social needs (i.e., social determinants of health collected during clinical care). This clinical decision support will appear during chart opening when a patient with blood pressure above goal presents in the clinic. The clinical decision support will include enhanced presentation of content, highlighting risks of undertreatment and providing guideline-concordant treatment intensification options. To facilitate the intensification of

treatment (when appropriate), the clinical decision support will also contain an embedded order set (i.e., a SmartSet) to prompt physicians to change or intensify medication based on practice guidelines. Templatized SmartText will also be embedded into the Notes section of the EHR to improve charting for hypertension patients. When providers sign off on patient notes, they may be prompted with requirements and recommendations for action items.

Patients who did not complete the SDoH screening pre-visit will be provided with a “SDoH Patient Handout” prior to collection of social determinants of health data during clinical care to introduce them to the type questions that will be asked and why their providers are collecting this information. This handout is currently used as part of clinical care at AAH.

Providers will have the opportunity to provide patient education materials (i.e., information to appear in the after-visit summary), which can be automatically ordered within the clinical decision support and are already available at Advocate. These will provide pre-templated instructions about treatment, current blood pressure values, and self-monitoring recommendations, such as using or buying blood pressure cuff, that are easily understood by all patient populations including those with low health literacy.

#### *6.2.4 Post-visit interventions*

We will streamline patient-subjects' access to the online patient portal by including information about the patient portal in the patients' after-visit summary and enabling providers to order nurse blood pressure check visits. Advocate has 24/7 online appointment scheduling capabilities that can be leveraged.

### **6.3 Schedule of visits**

There are no study-specific visits in this trial. We have outlined the time points in which data are collected below for implementation and evaluation of the interventions.

Data collection	Pre-randomization	Follow-up
EHR review for provider eligibility	X	
Provider characteristics (Demographics)	X	
Systolic blood pressure	X	X
Antihypertensive dosage	X	X
Resource use - Clinical encounters, using number of office visits, telephone calls and patient portal interactions	X	X

#### *6.3.1 Implementation evaluation*

As part of an implementation evaluation, several assessments will be conducted with the Advocate Aurora Health clinic personnel at the clinics which were randomized to the intervention arm.

##### **1. Provider Interviews**

We will conduct recorded phone or virtual interviews with consenting Advocate primary care providers who were randomized to the intervention arm to explore: (1) barriers to hypertension management, (2) experience with the study-specific EHR tools, and (3) opinions of sustainability of the intervention. Providers will be invited to participate via email (see attachment).

Prior to the interviews, providers will be asked to provide verbal informed consent for participation (see Fact Sheet attachment). Participants will not be forced to participate and may withdraw their consent to participate at any time. Participants will be informed that participation is voluntary and that the interviews are part of a research study.

Each interview will be conducted by an Advocate investigator and a BWH investigator. A semi-structured interview guide will be utilized (see attachment). Following provider interviews, the recordings will be transcribed. The transcriptions will be used to help evaluate the implementation of the intervention. We plan to interview approximately 15-20 providers.

2. Clinic manager survey followed by discussion at clinic manager meeting  
Clinic managers at each of the clinics assigned to the intervention arm will receive an email from Advocate leadership asking them to respond via email to a questionnaire (see attachment) regarding their experience implementing the study tools into the clinic workflow. They will also be invited to attend a regularly-scheduled clinic manager meeting that they currently already have scheduled as part of regular clinical care and management to provide additional feedback.

The responses to the clinic manager survey and discussion will be obtained by Advocate research staff, who will provide summary of these outcomes to the broader study team. No identifying information will be shared with Brigham and Women's Hospital study staff.

#### **6.4 Data sources and collection**

##### *6.4.1 Sources of research material, data that will be recorded, when data will be collected*

Data regarding patients' medical history, disease control, medication use and health care utilization will be obtained from AAH EHR data or pharmacy dispensing data for analysis of the trial. De-identified transcripts of recordings from patient and provider interviews will also be used for qualitative analysis for Aim 1 (interviews previously conducted under the IRB approval of Advocate Aurora Health).

The Advocate data warehouses reside in an Oracle 9i environment and consists of the Clarity and Payer databases. The Clarity database is a relational database that contains clinical and financial information from the Epic Suite of products; including the electronic medical record system (EpicCare), the appointment scheduling system (Cadence), the patient accounting system (Resolute), the patient web portal and the master patient index (Identity). The various tables within the Clarity database are refreshed on a daily, weekly or monthly basis.

These data are listed in the Attachments.

##### *6.4.2 Linkages to subjects, access to subject identities*

Individually identifiable data are maintained for patient care purposes within the Advocate Network and is needed to identify patients and to monitor care recommendations by providers. Without this linkage, we could not fulfill the study's objectives. To protect the confidentiality of these data, only the provider group's data analyst and project manager will have access to personal identifiers while linking the data and constructing study variables for the trial. After linkage is completed and study variables are created, all identifiable information will be deleted from the study database. All data transfers between the organizations will be accomplished using secure file transfer protocols. Only HIPAA-limited data will be

shared with the study team based at Brigham and Women's Hospital, who are all properly trained in research management and approved by the IRB. All personally identifiable health information will be kept under lock and key. The only HIPAA identifiers that will be received by the study team at Brigham and Women's hospital are dates, which are necessary for the evaluation of study outcomes (e.g., change in systolic blood pressure between certain dates.)

### **6.5 Study endpoints**

The trial will be completed 24 months after trial launch. At the end of the study period, data will be extracted retrospectively from electronic health records; the primary analysis will be on patients who visited one of the 24 clinics during the study period and who meet the inclusion criteria.

Primary:

- Change in systolic blood pressure from patient identification (i.e., the most recent encounter that identified the patient as eligible) through 12-month follow-up, using values recorded in the EHR

Secondary:

- Percentage of patients with well-controlled blood pressure (<140/88mmHg) or <130/80 mmHg for those with comorbid conditions defined by clinical guidelines at 12 months follow-up, using values in the EHR
- Percentage of patients with intensification of medication in the 12-month follow-up period, defined by addition of therapy or increasing dose
- Percentage of patients with guideline-concordant medications ordered in the 12-month follow-up period
- Change in the gap in systolic blood pressure between each of Black and Hispanic/Latino patients and non-Hispanic White patients from the last encounter before identification through 12 months after, using values in the EHR
- Change in diastolic blood pressure from the encounter before identification through 12 months after, using values recorded in the EHR

Exploratory:

- Frequency of viewing the dashboard, SmartSet order set, documentation choices, and acknowledgement reasons
- Intervention fidelity: BPAs (alerts) firing as intended

Clinical encounters, using number of office visits, telephone calls and patient portal interactions between AAH primary care providers and patients during the 12-month follow-up period. These outcomes will also be measured in the remainder of the follow-up period until the end of administrative censoring at the end of the 2-year trial.

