## 2. Specific Aims and Objectives

The overall goal of this project is to improve existing decision support for hypertension control and to reduce disparities in treatment, consistent with professional guidelines and quality metrics. To achieve this, we will **conduct and evaluate a cluster randomized trial to determine whether health IT tools targeted to providers improve blood pressure control for patients with uncontrolled hypertension.**

Our primary hypothesis is that a health IT intervention will improve systolic blood pressure (primary outcome), concordance with hypertension guidelines (secondary outcome), diastolic blood pressure (secondary outcome), treatment intensification (secondary outcome), and post-visit patient-provider follow-up (tertiary outcome) compared with usual care.

The objectives and endpoints are summarize below:

OBJECTIVES	ENDPOINTS	JUSTIFICATION FOR ENDPOINTS
Primary		
To determine whether multicomponent EHR-based health IT tools designed using behavioral	Change in systolic blood pressure from identification to 12-month follow-up, using values in the EHR	These outcomes are rapidly measurable using EHR data and will provide evidence of blood pressure control.

Mass General Brigham Institutional Review Board  
Intervention/Interaction Detailed Protocol

OBJECTIVES	ENDPOINTS	JUSTIFICATION FOR ENDPOINTS
principles targeted at providers improve blood pressure control for patients with uncontrolled hypertension as compared with usual care (no intervention).		
Secondary		

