#### 3.2 Overall design

**In the first Phase (Aim 1),** we will analyze 30 de-identified qualitative interview transcripts that were conducted with 15 patients and 15 providers (14 primary care physicians and 1 medical assistant) from two AAH primary care clinics to understand perspectives on hypertension management and identify opportunities to improve EHR tools for providers. The interviews were previously conducted between October 2020 and March 2021 under the oversight and approval of the Advocate Aurora Health IRB. In brief, treating physicians provided approval for potential patient participants to be contacted. Eligibility criteria for the interviews included a diagnosis of hypertension and seeking care at one of the two pilot practices. After approval, patients were contacted for their willingness to be interviewed and consent was obtained using a fact sheet. Providers were eligible for the interviews based on their practicing as clinicians in the pilot practices. Each interview was conducted using an approved semi-structured interview guide and were audio-recorded and subsequently transcribed. Participants were offered compensation for their time. All data were previously de-identified. We are seeking approval by the MGB IRB for the analysis of the de-identified data collected during these interviews.

**In the second Phase,** we will conduct a 2-arm pragmatic cluster randomized clinical trial to evaluate whether a multicomponent health IT intervention improves blood pressure control and reduces racial/ethnic disparities. Participating clinics will be randomly assigned to one of 2 arms: (a) Arm 1: multicomponent, intervention and (b) Arm 2: usual care (i.e. no intervention). Providers and in each arm will receive the same intervention for up to 24 months after randomization, which will allow us to determine the relative effectiveness of each approach as well as their long-term impact on clinical outcomes. Primary care providers in the intervention clinics will receive electronic decision support tools to guide their care of eligible patients. Providers in usual care clinics will receive usual care at AAH. Patients will not receive any intervention or outreach independent of their provider or care team. We will use EHR data to implement the EHR tools, identify study subjects, track study progress, and evaluate the effect of the interventions.

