#### 3.3 Study schema

## 4. Subject Selection

### 4.1 Inclusion Criteria

The trial will include provider subjects with eligible patients. Specific decision support at the point of care will also appear for patients whose latest outpatient/ambulatory blood pressures are elevated (i.e.,  $SBP \geq 140$  or  $DBP \geq 90$ ). There is no upper limit for SBP or DBP, as this cutpoint is driven by HEDIS criteria and would otherwise exclude patients who may be in greatest need of care. Limited inclusion criteria will be applied to maximize generalizability in accordance with pragmatic trial principles outlined by PRECIS-2 (Pragmatic Explanatory Continuum Indicator Summary). The patient population will only be included for the purpose of providers receiving decision support and for the purpose of analyzing the effect of the intervention. The study criteria are defined below.

**Provider-subjects** will receive EHR interventions if they are primary care providers (internal medicine, family medicine, geriatrics) employed by AAH at one of the 24 participating clinics cluster randomized to the intervention.

**EHR patient data will be collected retrospectively** for analysis and used for the EHR tools for providers based on the following criteria:

1. Medical Group Medical Home Population: 1 visit with PCP in past 2 years (rolling 24 months) and Patient has a medical group PCP as their EPIC General PCP
2. Current age 18-85 years

3. Hypertension diagnosis on EPIC Problem list OR at least 2 visits (office/telehealth/telephonic) with an encounter diagnosis of HTN on different dates, with at least one during the last 24 months (rolling dates)
4. Latest outpatient/ambulatory (exclude urgent care) SBP  $\geq 140$  or DBP  $\geq 90$  (12 months rolling) (lowest measure if more than one taken at the same time) (no upper limit)

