#### 4.2 Exclusion Criteria

Providers and patients not meeting the inclusion criteria above will not be included in the analysis of the trial. No other exclusion criteria will be used.

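### The primary endpoint's index date and horizon are inconsistent: the plan gives three start dates, and on the visible text patients identified after month 12 cannot have a full 12-month window

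*Combined protocol and SAP*

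**What the plan says.** On who is analysed, section 6.5 states that "the primary analysis will be on patients who visited one of the 24 clinics during the study period and who meet the inclusion criteria". Section 4.2 adds: "No other exclusion criteria will be used".

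On timing, 6.5 says "The trial will be completed 24 months after trial launch" and plans a single retrospective pull of the records at that point. Section 3.2 says that providers "will receive the same intervention for up to 24 months after randomization".

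On the outcome, the section 2 table gives "Change in systolic blood pressure from identification to 12-month follow-up, using values in the EHR". Section 6.5 repeats this and glosses identification as "the most recent encounter that identified the patient as eligible".

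Other sections place the start of follow-up elsewhere. Section 6.2.2 identifies a patient at the first visit to a trial clinic and requires that visit to be in person for the primary analysis. Section 9.2 powers the trial for a change counted from randomisation. Section 6.3 lists SBP collection before randomisation and at follow-up. The section 2 table refers to a 24-month follow-up period for some secondary and exploratory outcomes.

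On missing data, section 9.3 plans multiple imputation if more than 10% is missing, sensitivity analyses with other methods, and a secondary longitudinal model that uses repeated SBP values.

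**The concern.** Two things are unsettled. The first is the index date, which fixes both the baseline SBP and the 12-month clock. Three start points are in play. Data are pulled retrospectively at month 24, so an analyst who takes the 6.5 gloss literally could select each patient's latest qualifying encounter. For a patient seen several times, baseline would then fall after the provider had already used the tools.

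The second is the horizon. Entry during the whole study period, a data cut at month 24 and a 12-month outcome cannot all hold for every patient. Someone identified after month 12 can supply only a shorter-horizon change or a value imputed for a date beyond the cut. Such an imputed value would also describe a time after the intervention period given in 3.2. The plan does not say which applies, nor which SBP reading counts as the 12-month value.

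What is at stake is the meaning of the primary estimate. Two analysts following this text could build different cohorts with different baselines and horizons, and the pooled figure need not be the stated 12-month effect.

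**Working it through.** **1. The plan's power figure.** Inputs from 9.2: difference 5.0 mmHg, SD 13.5, alpha 0.05 (two-sided assumed), ICC 0.1, 24 clinics, 49395 patients. From 5.2: equal allocation, so 12 clinics per arm. Equal clinic sizes are assumed.

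- m = 49395/24 = 2058 patients per clinic.
- SE = 13.5 × sqrt(2 × (0.1 + 0.9/2058)/12) = 1.747.
- Power (normal) = Φ(5.0/1.747 − 1.96) = 81.7%, which agrees with the stated figure of more than 80%.
- With a t reference on 22 df it is 78.1%. That shortfall is a separate matter from this point.

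**2. The index dates side by side.** Take a hypothetical patient first seen with raised SBP at month 3 and seen again, still raised, at month 15.

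| Source | Index month | 12-month window closes | Observable by month 24? |
|---|---|---|---|
| 9.2 (randomisation, taken as launch) | 0 | 12 | yes |
| 6.2.2 (first visit) | 3 | 15 | yes |
| 6.5, literal reading at extraction | 15 | 27 | no, 24 − 15 = 9 months |

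In the last row, baseline comes 15 − 3 = 12 months after the first qualifying visit.

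**3. Observable time.** For identification at month t, observable time is 24 − t. Months 12, 15, 18 and 21 give 12, 9, 6 and 3 months. This step needs no assumption beyond the 6.5 text.

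**4. Share identified late (illustration only).** The documents give no visit rate. Assume everyone is eligible from launch, qualifying visits follow a Poisson process at r per year, and entry is at the first visit.

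- Share after month 12 among those seen by month 24 = exp(−r)/(1 + exp(−r)).
- Mean observable months for these patients = 12 × (1 − 1/r + exp(−r)/(1 − exp(−r))).
- If a 5.0 mmHg effect built up linearly over 12 months, the pooled mean = 5.0 × (1 − share × (1 − months/12)).

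| r per year | Share late | Mean months observable | Pooled mean, mmHg |
|---|---|---|---|
| 0.5 | 38% | 6.5 | 4.1 |
| 1 | 27% | 7.0 | 4.4 |
| 2 | 12% | 7.9 | 4.8 |
| 3 | 5% | 8.6 | 4.9 |
| 4 | 2% | 9.2 | 5.0 |

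With an immediate effect the pooled mean stays at 5.0. Identification spread uniformly over 24 months would give a late share of 50%. Departures from the model could move the share either way. If values beyond the cut were counted as missing, any late share above 10% would trigger the imputation rule in 9.3 through the calendar alone.

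**5. Power cost of a full-window cohort.** If half the patients are kept, m = 1029, SE = 13.5 × sqrt(2 × (0.1 + 0.9/1029)/12) = 1.750, and power is 81.5% (normal) or 77.9% (t, 22 df). The loss is about 0.2 points on either scale, because clinic count and ICC dominate the standard error.

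**The case against.** The strongest reply is that a cohort anchored near launch may be intended. Pre-randomisation SBP in 6.3, the 24-month follow-up period in section 2, the randomisation start in 9.2, and the 9.3 plan to follow outcomes past an initial 12 months up to month 24 all fit that reading. The rolling dates in 4.1 are look-backs for eligibility and do not say that entry continues to month 24. This stands as a reason to call the wording inconsistent. It does not remove the problem, because 6.2.2 and 6.5 date identification at a visit and 6.5 admits visits throughout the study period.

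Next, through 12 months may mean any SBP observed up to 12 months, so that late patients contribute what they have. Section 6.5 also mentions administrative censoring at the end of the trial, though for the encounter outcomes. This is a possible reading, but no such rule is written for SBP. It would also mix horizons under a 12-month label.

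The 6.5 gloss may likewise mean the most recent encounter as of identification, which would agree with 6.2.2. A baseline after exposure is therefore a risk of the literal reading and not a settled feature of the plan.

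A last identification date may also sit in text that could not be seen: between 5.2 and 6.2, in the 3.3 schema, or in the Attachments. That limit stands.

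Finally, the blinding in 9.3 limits outcome-driven choices, and the sensitivity analyses and longitudinal model help in part. None of them defines the primary cohort or its horizon.

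**Conclusion.** The concern holds as a defect in how the primary effect is defined, and it should be fixed before the data are extracted. Two findings follow from the plan's own text: the start dates conflict, and on the visible text a patient identified at month t > 12 has only 24 − t months observable. The second assumes that no unseen section sets a last identification date.

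The number of patients affected is unknown. The 2% to 38% range and the pooled means of 4.1 to 5.0 mmHg rest on assumed visit rates and an assumed linear build-up, and show only that the share could be trivial or substantial.

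A reader might infer that the design knowingly admits patients too late, that the primary result will be biased, or that late entrants can contribute nothing. The documents do not support these readings. Several passages suggest follow-up from launch, nothing shows that late entry differs between arms, and late entrants could contribute observed values if a rule said so. Lost sample size is not the issue either.

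**What to change.** In section 6.5:

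1. Anchor baseline SBP and the 12-month clock to the first qualifying in-person visit after launch, and bring 6.2.2, 6.3 and 9.2 into line with it.
2. Estimate the 12-month effect in patients whose window closes by the data cut. State that values beyond the cut are not imputed as ordinary missing data. Report alongside it an analysis of all identified patients using SBP observed up to 12 months or administrative censoring, for example with the longitudinal model already planned in 9.3, and show the spread of horizons by arm.
3. State which SBP reading, within what window, counts as the 12-month value.

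If a section not seen here already sets a last identification date, repeat it in 6.5.

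The drafting cost is a few sentences and a date filter, and the power cost is about 0.2 points even if half the patients leave the primary cohort. The real cost is selection, because a full-window cohort under-represents people who attend rarely. Section 1 says that minority patients return to care less often, so this touches generalisability and the disparity endpoint. If one group made 1 qualifying visit a year and another 2 (assumed), the full-window rule would drop 27% against 12%. The all-patient analysis is needed for that reason and should not be left optional.

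Extracting data later would complete the windows without excluding anyone. Late entrants would still have less than 12 months of intervention under the period stated in 3.2, so the plan would have to say what that estimate means.

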To determine whether multicomponent EHR-based health IT tools designed using behavioral principles targeted at providers improve concordance with hypertension guidelines, diastolic blood pressure control, and treatment intensification compared with usual care.	
Percentage of patients with well-controlled blood pressure (<140/88mmHg) at 24 months follow-up, using values in the EHR.
 
Percentage of patients with intensification of medication in the 24-month follow-up period, defined by addition of therapy or increasing dose.
 
Percentage of patients with guideline-concordant medications ordered in the follow-up period.
 
Change in the gap in systolic blood pressure between Black and Hispanic/Latino patients and non-Hispanic patients from identification to 12-month follow-up
 
Change in diastolic blood pressure from identification to 12-month follow-up
	These outcomes capture the extent to which there is an improvement in concordance with hypertension guidelines, diastolic blood pressure control, and treatment intensification during the follow-up period.
Exploratory		
To better understand patient and provider's perspective on hypertension management through the AAH healthcare system	Analysis of de-identified qualitative interviews including patients and providers from AAH primary care sites	These outcomes will inform the research methods and health IT tool design for the pragmatic cluster randomized trial.
To determine whether multicomponent EHR-based health IT tools designed using behavioral principles targeted at providers improve post-visit patient-provider follow-up compared with usual care.	Clinical encounters, using number of office visits, telephone calls and patient portal interactions between AAH primary care providers and patients during the 24-month follow-up period	These outcomes measure the post-visit patient-provider follow-up during the follow-up period.
To assess the implementation of the intervention in practices	Adoption of the EHR interventions and integration of the intervention into clinics	These outcomes will be used to evaluate aspects of the implementation of the intervention and will provide valuable information regardless of the clinical results of the trial.

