### 6.2.2 Pre-visit interventions

Providers in the intervention arm will receive an EHR-embedded dashboard which will highlight racial/ethnic differences in rates of achieving blood pressure control within their patient panel. Using EHR data, we will identify eligible patients: (1) Medical Group Medical Home Population: 1 visit with PCP in past 2 years (rolling 24 months) and Patient has a medical group PCP as their EPIC General PCP, (2) current age 18-85 years, (3) hypertension diagnosis on EPIC Problem list OR at least 2 visits (office/telehealth/telephonic) with an encounter diagnosis of HTN on different dates, with any during the last 24 months (rolling dates) performing provider, and (4) latest outpatient/ambulatory (exclude urgent care) SBP  $\geq$ 140 or DBP  $\geq$ 90 (12 months rolling) (lowest measure if more than one taken at the same time).

Among these eligible patients, patients included in the primary analysis will be those that had an in-person visit at one of the trial clinics. This is because the primary decision support aimed at providers is based on office visits. Patients are first identified as eligible for this analysis based on the first time that they had a visit at one of trial clinics. The dashboard will also provide individual-level information for patients with poorly-controlled blood pressure including (a) most recent blood pressure values, (b) current therapies (based on the medication list), (c) next scheduled appointment, and (d) social determinant needs. Patients in the intervention arm will receive outreach via MyChart, a component of the patient portal, to answer questions regarding their social determinants of health (SDoH).

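### The blood pressure change endpoints have conflicting time origins, and the primary endpoint's wording permits a post-exposure baseline if coded as the last qualifying encounter

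*Combined protocol and SAP*

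**What the plan says.** Section 6.5 defines the primary endpoint as SBP change "from patient identification (i.e., the most recent encounter that identified the patient as eligible) through 12-month follow-up". Section 6.2.2 says: "Patients are first identified as eligible for this analysis based on the first time that they had a visit at one of trial clinics".

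For two secondary endpoints, 6.5 uses another origin. DBP is "Change in diastolic blood pressure from the encounter before identification through 12 months after", and the racial/ethnic SBP gap runs "from the last encounter before identification through 12 months after, using values in the EHR". The objectives table in section 2 starts all three at identification, which it does not define: "Change in systolic blood pressure from identification to 12-month follow-up, using values in the EHR" for SBP, "Change in diastolic blood pressure from identification to 12-month follow-up" for DBP, and likewise for the gap. The power statement in 9.2 counts its 12 months from randomization.

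Four other statements bear on how these sentences would be coded:
- The trial ends 24 months after launch, and 6.5 adds: "At the end of the study period, data will be extracted retrospectively from electronic health records".
- Criterion 4 in 4.1 rests on the latest outpatient reading in a rolling 12 months (SBP at least 140 or DBP at least 90), so a patient can qualify more than once.
- The decision support in 6.2.3 opens whenever an above-goal patient presents, so a repeat qualifying visit in the intervention arm follows exposure.
- Under 6.4.2, study variables are constructed on the provider group's side before the data reach the analysis team.

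**The concern.** The sentence that defines the primary endpoint does not say as of what date an encounter is the most recent one. With all 24 months of records in hand, a programmer could take it to mean the last encounter in the study at which the patient qualified. Three things would follow.

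1. For anyone who qualified more than once, baseline would come after exposure began, so part of the effect would already be in it.
2. Any later trial-clinic reading that met the cut would itself have become the baseline. The remaining follow-up readings are therefore below the cut by construction, in both arms.
3. Whether a later reading exists would depend on not qualifying again, which is what the intervention aims to change. Missing outcomes would then differ by arm.

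The main risk is that a real effect is missed because of which sentence was coded. The different origins for DBP and the gap matter less: if identification is the first visit, they do not by themselves bias the arm comparison, but they make within-arm changes non-comparable across endpoints.

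**Working it through.** **1. The plan's own figure.** From 9.2: difference 5.0 mmHg, SD 13.5, ICC 0.1, alpha 0.05, 24 clinics, 49,395 patients. From 5.2: equal allocation, so 12 clinics per arm. Two-sided alpha, equal clinic sizes and a normal approximation are assumed.
- Mean clinic size: 49,395 / 24 = 2,058.
- Design effect: 1 + (2,058 - 1) x 0.1 = 206.7.
- SE = sqrt(2 x 13.5^2 x 206.7 / (12 x 2,058)) = sqrt(3.05) = 1.75 mmHg.
- Power = Phi(5.0/1.75 - 1.96) = Phi(0.90), about 82%.

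The stated power above 80% reproduces.

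**2. The origins side by side.**

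| Endpoint | Section 6.5 | Objectives table | Elsewhere |
|---|---|---|---|
| SBP change (primary) | most recent qualifying encounter | identification | 6.2.2: first trial-clinic visit; 9.2: randomization |
| DBP change | encounter before identification | identification | none |
| SBP gap | last encounter before identification | identification | none |

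Several statements favour a first-visit index. One is 6.2.2 itself. Another is that 12 months of follow-up must fit inside a 24-month trial. Section 6.5 adds "These outcomes will also be measured in the remainder of the follow-up period until the end of administrative censoring", section 9.3 looks past the initial 12 months up to month 24, and 6.3 lists SBP before randomization.

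**3. A late origin, without selection.** If the effect builds linearly over B months and the origin falls d months after first exposure, the share retained is 1 - d/B. With B = 12 and d = 6, it is 1 - 6/12 = 50%. With B = 6 and d = 3, it is also 50%.

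**4. Adding selection, by simulation.** None of these inputs is in the documents:
- patient mean SBP 135, 142 or 150;
- between- and within-patient SDs both 10 or both 12;
- visits every 3, 4 or 6 months;
- full effect 5 mmHg, with five onset shapes (immediate; linear over 6, 12 or 24 months; half the effect per alert, up to two);
- SBP criterion only, no clustering, 80,000 patients per arm;
- outcome either the last reading within 12 months or the reading nearest month 12 within months 9-15.

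Loss = 1 - (difference with the later origin / difference with the first-visit origin), under the same onset and outcome rule.

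| Origin | Result |
|---|---|
| First qualifying visit, immediate onset | -4.8 to -5.2 mmHg |
| Last qualifying encounter in 24 months, immediate onset | 55-96% lost |
| Same, all five onset shapes | 45-99% lost |
| Same, visits every 8-12 months (immediate or 12-month onset) | 52-80% lost |
| Last qualifying encounter in months 0-12, immediate or 6-month onset | 49-89% retained |
| Same, per-alert onset | 50-105% retained |
| Same, 12-month onset | 65-107% retained |
| Same, 24-month onset | 108-133% retained |

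A second simulation used different inputs (mean 135-145, between-patient SD 6-13.5, within-patient SD 8-13, mean visit gap 2-6 months, build-up 0-12 months). The last-encounter origin lost 54-88%. In one of its scenarios (mean 145, both SDs 10, mean visit gap 4 months, immediate effect) the difference was -5.03 mmHg from the first visit and -0.83 from the last qualifying one. Retained: 0.83/5.03 = 17%, so 83% was lost.

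**5. Missing follow-up.** In the main simulation with the last-reading rule, the literal reading left 46-79% of control and 32-72% of intervention patients with no reading in the 12 months after baseline. The first-visit index left 0-9%. With irregular visit gaps the first-visit figure was 2-21%, equal between arms. The literal-reading shares all exceed the 10% at which 9.3 calls for multiple imputation.

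**The case against.** The strongest answer is that the damaging reading is not the natural one. Criterion 4 already works with a latest reading on a rolling window, and 6.2.2 places identification at the first trial-clinic visit. The encounter that most recently made the patient eligible then means the latest qualifying reading as of that visit, and the DBP and gap wording can be read the same way. A last-in-study origin would also leave many patients without 12 months of follow-up, which defeats its own sentence. The objectives table is introduced as a summary, and the phrase in 9.2 describes a power assumption.

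Most of this stands. It shows what the sponsor probably intends, so a reader should not infer that the trial will in fact use a post-exposure baseline. It does not remove the conflict: 6.5 is where the primary endpoint's identification is spelled out, and it gives no as-of date.

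It is also fair that every simulation input is assumed, that qualification through DBP was not modelled, and that the loss shrinks or vanishes if the origin is confined to months 0-12.

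A further limit concerns bias. The intervention lets providers order nurse blood pressure checks (6.2.4), so visit frequency may differ by arm. In a simulation with no true effect, and assumed visits every 3-4 months in the intervention arm against every 6 in control, the first-visit index gave -0.2 to -1.1 mmHg and the literal rule +0.2 to -0.4. So the first-visit index cannot be called unbiased without condition, nor can the literal rule be said never to create an apparent effect.

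Finally, the schema in 3.3, the data attachments cited in 6.4.1 and section 6.1 are not in the text available here and may already settle the rule.

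**Conclusion.** The conflict is real and lies in the definition of the primary endpoint. It should be resolved before extraction, but it is not a fatal flaw: the plan as a whole favours a first-visit index with the latest qualifying reading as of that visit as baseline, and that is sound when visit patterns are similar in the two arms.

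The size is conditional. If the last qualifying encounter of the whole study is coded, roughly half to nearly all of a real 5 mmHg effect would be lost under the assumed inputs. If the origin is limited to months 0-12, the loss runs from none to about half. No figure for this loss appears in the documents.

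A reader might also infer that the trial is underpowered. The documents do not support that: on 9.2's own inputs, power is 82%. Nor is an effect size after imputation claimed, because 9.3 names multiple imputation without specifying a model.

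**What to change.** In 6.5, replace the most-recent-encounter wording with one rule:
- **Index date:** the first in-person trial-clinic visit on or after launch at which criteria 1-4 of 4.1 are met, one per patient, never reset.
- **Baseline:** one named reading at or before that visit, for example the reading that met criterion 4 as of that visit.
- **12-month value:** one named reading, for example the one nearest month 12 within a stated window.
- **Scope:** the same origin for SBP, DBP and the SBP gap.

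Align the objectives table, 6.2.2, 6.5 and 9.2 with this rule. If the schema, a data attachment or another section already fixes it, copy that text into 6.5.

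The cost is protocol and SAP wording plus one extraction rule. No new data are needed, provided it is settled before extraction and unblinding.
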